#### 4.1.1.3. Missing Time

If time is missing for a laboratory assessment taken on the first day of IMP administration, ie Day 1, but the time of IMP administration is available, then time for the laboratory assessment will be assumed to have occurred prior to IMP administration and will serve as the baseline value, assuming that the timepoint for the assessment was designated as predose. If the timepoint for the assessment was designated as postdose, then the assessment will be assumed to have been taken postdose.

#### 4.1.1.4. Imputation for Alphanumeric Data

Should there be instances where a clinical laboratory parameter is reported with imbedded non-numeric characters, as for example, “<0.1” or “>10”, the data will be imputed for quantitative summaries. The actual values as reported in the database will be presented in data listings.

For incorporation in quantitative summaries, the following imputation rules will be employed: the lower limit of quantification will be replaced with  $\frac{1}{2}$  the value of the lower limit. For example, < 0.1 will be replaced with 0.05.

The upper limit of quantitation will be increased by one level of precision that precedes the value. For example, “>0.1” will be imputed to “0.11”, and “>10” will be imputed to “10.1”.

Additionally, the upper limit of normal (ULN)/lower limit of normal (LLN) values may be reported as alphanumeric (eg, ‘<5’, ‘≤5’, ‘>5’, ‘≥5’). In these cases, if the ULN or LLN is necessary for determination of the laboratory severity grade, the following conventions will be employed:

If the value is in the form of  $\leq 5$ , the ULN will be populated with the value after removing the symbol (ie, the ULN is set to 5). If the value is in the form of  $<5$ , the ULN will be decreased by two levels of precision in the direction of the symbol (ie, the ULN is set to 4.99).

If the value is in the form of  $\geq 5$ , the LLN will be populated with the value after removing the symbol (ie, the LLN is set to 5). If the value is in the form of  $>5$ , the LLN will be increased by two levels of precision in the direction of the symbol (ie, the LLN is set to 5.01).

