10.2. Appendix 2: Clinical Laboratory Tests

The tests detailed in Table 12 will be performed by the local laboratory.

Protocol-specific requirements for inclusion or exclusion of participants are detailed in Section 5.

Additional tests may be performed at any time during the trial as determined necessary by the investigator or required by local regulations.

Participants must have COVID-19 testing done with a negative test result within a maximum of 5 days prior to, but as close as possible to each admission to the clinic. COVID-19 testing may be performed after admission per the investigator's discretion.

Table 12: Protocol-Required Safety Laboratory Assessments

Laboratory Assessments	Parameters	
Hematology	Platelet count RBC count Hemoglobin Hematocrit Prothrombin time and INR MCH MCHC MCV	WBC count with differential (absolute and %): Neutrophils Lymphocytes Monocytes Eosinophils Basophils
Chemistry	BUN Creatinine Glucose Albumin Cholesterol (total, HDL, LDL) Triglycerides Uric acid Potassium Sodium Calcium Bicarbonate Chloride Magnesium Phosphorus	ALT AST Alkaline phosphatase GGT CPK Total bilirubin and direct bilirubin Total protein
Routine Urinalysis	Urine dipstick with reflex to microscopy if positive finding Specific gravity pH, glucose, protein, blood, ketones, bilirubin, urobilinogen, nitrite, leukocyte esterase by dipstick Serum Cystatin-C	
Additional Required Tests	Urine β-2-microglobulin	
Other Screening Tests	A confirmatory FSH is required for post-menopausal women. Breathalyzer or blood/urine test for alcohol and urine drug screen (including cotinine) Serology (HIV, HBsAg, HBcAb, Hepatitis C Ab) SARS-CoV2 testing Thyroid-stimulating hormone with reflex to free T4 if abnormal	

Abbreviations: Ab=antibody; Ag=antigen; ALT=alanine aminotransferase; AST=aspartate aminotransferase; BUN=blood urea nitrogen; CPK=creatine phosphokinase; FSH=follicle stimulating-hormone; GGT=gamma glutamyl transferase; HBc=hepatitis B core; HBsAg=hepatitis B surface; HDL=high-density lipoprotein; INR=international normalized ratio; LDL=low-density lipoprotein; MCH=mean corpuscular hemoglobin; MCHC=mean corpuscular hemoglobin concentration; MCV=mean corpuscular volume; RBC=red blood cell; SARS-CoV2=severe acute respiratory syndrome coronavirus 2; T4=thyroxine; WBC=white blood cell.

Investigators must document their review of each laboratory safety report and file appropriately.

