10.6. Appendix 6: Kidney Safety for First-in-Human Trial

10.6.1. Elevations in Serum Creatinine

Serum creatinine (SCr) level may be affected by age, muscle mass, diet, activity, and tubular transporter activity, and SCr elevations can occur without impacting overall kidney function. Nonetheless, kidney function is closely monitored using blood urea nitrogen (BUN), serum creatinine, and urinalysis.

Table 20: Monitoring of Abnormal Kidney Function Tests

Lab Result	Action
Serum creatinine > ULN	Repeat for confirmation approximately 1 hour after drinking a large glass (~250 mL) of water
Urinalysis (UA) • ≥+1 protein • + glucose	Repeat for confirmation approximately 1 hour after drinking a large glass (~250 mL) of water
Active urine sediments (eg, hematuria, pyuria, casts [WBC, RBC, tubular epithelial, or granular])	

Abbreviations: RBC=red blood cell; ULN=upper limit of normal; WBC=white blood cell.

Contact the medical monitor if the repeat confirmation SCr >1.2× ULN or urine continues to have proteinuria, glucosuria, or active urine sediments.

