## 5. STATISTICAL ANALYSIS METHODS

### 5.1. General Considerations

Descriptive statistical methods will be used to summarize the data from this study. No formal hypothesis testing is planned for this trial. Unless stated otherwise, the term “descriptive statistics” refers to number of subjects (N), number of observations (n), mean, median, standard deviation (SD), Q1, Q3, minimum, and maximum for continuous data and frequencies and percentages for categorical data. Figure presentations will include appropriate variability indicator such as SD or standard error (SE).

All data collected during the study will be included in data listings. Unless otherwise noted, the data presentations will be sorted first by trial part (A or B), cohort, and subject number. Unless otherwise noted, summary tables will be separated into Part A Cohorts 1 and 2, Part A Food Effects, and Part B.

In Part A, the term “treatment sequence” refers to the sequence of treatment for each individual. “Treatment group” refers to treatment with CVL-354, at different doses, or placebo. Since Part A is a crossover study, subjects will appear in multiple groups. For Part A Cohorts 1 and 2, “Treatment period” refers to Periods 1 through 4 described in [Figure 1](#). For Part A Food Effects, “Treatment period” refers to Period 1 and 2 described in [Figure 2](#).

In Part B, “treatment group” refers to treatment with CVL-354, at different doses, or placebo QD or BID. Doses will be determined based on data from Part A.

For summary presentations, placebo subjects will be combined across cohorts within a given Part.

The statistical analyses will be conducted with the SAS® software package Version 9.4 or higher.

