#### 5.9.4. Clinical Laboratory Assessments

Descriptive summaries of selected (quantitative) clinical laboratory results will be presented by study day and treatment group. Laboratory values outside the normal range for each parameter will be identified using shift tables. Each subject's hematology, blood chemistry, and quantitative urinalysis values will be flagged as "low" (below the lower limit of normal/LLN), "normal" (within the normal range), or "high" (above the upper limit of normal/ULN) relative to the normal ranges of the central laboratory. Each subject's qualitative urinalysis values will be flagged as "normal" or "abnormal". Shifts from baseline, or period baseline if Part A, to high/normal/low status for hematology and blood chemistry parameters that are not CTCAE graded will be presented to the maximum post-baseline/post-period baseline value and the minimum post-baseline/post-period baseline value for each laboratory test. Shifts from baseline, or period baseline if Part A, to normal/abnormal status for urinalysis parameters that are not CTCAE graded will be presented to the maximum post-baseline/post-period baseline value and the minimum post-baseline/post-period baseline value for each laboratory test. Otherwise, for hematology, blood chemistry, and urinalysis parameters that are CTCAE graded, laboratory toxicities will be programmatically graded by severity using Cerevel's modified CTCAE Version 5.0. Shifts from baseline, or period baseline if Part A, to greatest (worst) treatment-emergent laboratory toxicity will be presented.

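### SAP 4.1.1.4 halves every '<x' laboratory result without exemption, which gives invalid values for urine specific gravity and pH if such a result is reported and summarised

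*SAP*

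**What the plan says.** SAP 4.1.1.4 sets a contingency rule. It opens with "Should there be instances where a clinical laboratory parameter is reported with imbedded non-numeric characters" and says that such data will be imputed for quantitative summaries. On the low side the substitute is half "the value of the lower limit. For example, < 0.1 will be replaced with 0.05". On the high side, "The upper limit of quantitation will be increased by one level of precision that precedes the value", so that '>10' becomes 10.1. No parameter is exempted from either rule. Listings are protected: "The actual values as reported in the database will be presented in data listings".

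The Routine Urinalysis row of Protocol Table 12 (Section 10.2) contains "Specific gravity pH, glucose, protein, blood, ketones, bilirubin, urobilinogen, nitrite, leukocyte esterase by dipstick". Specific gravity and pH are therefore protocol laboratory parameters.

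SAP 5.9.4 states: "Descriptive summaries of selected (quantitative) clinical laboratory results will be presented by study day and treatment group". It does not name the selected results. It does refer to quantitative urinalysis values, in the sentence on low/normal/high flagging. Under SAP 5.1, a descriptive summary means the "number of observations (n), mean, median, standard deviation (SD), Q1, Q3, minimum, and maximum for continuous data".

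**The concern.** Half the limit is a reasonable stand-in for a censored concentration, because the true value lies somewhere between zero and the limit. It fails on a scale that does not extend towards zero. Specific gravity is measured relative to water at 1.000, so half of any plausible reporting limit lies far below the attainable range. Halving a urine pH limit gives a number that is not impossible in itself but is implausible for urine.

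A programmer who follows SAP 4.1.1.4 as written would apply the halving, because the trigger is the presence of a non-numeric character and not the type of analyte. In groups of 6 to 16, one such value would dominate the mean and SD and would appear as the minimum. At stake is the validity of a descriptive safety table. No decision rule is involved.

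**Working it through.** **1. Reproduce the SAP's own examples.** '<0.1' gives 0.1/2 = 0.05. '>0.1' gives 0.11 and '>10' gives 10.1 after one digit is added. All three match SAP 4.1.1.4, so the rule has been read correctly.

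**2. Apply the rule to assumed results.** The documents give no reporting limits, so these are assumptions.
- Specific gravity '<1.005': 1.005/2 = 0.5025. With '<1.001' instead: 0.5005.
- Urine pH '<5.0': 5.0/2 = 2.5.
- High side, for contrast: '>1.030' becomes 1.0301, a negligible change.

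**3. Group sizes from the documents.**
- Part A single ascending dose: 8 per cohort at 3:1, so 8 × 3/4 = 6 on active drug per period.
- Part B: 8 active and 2 placebo per cohort.
- Placebo is pooled within each Part (SAP 5.1). Part B has up to 5 × 2 = 10. Part A Cohorts 1 and 2 have 2 cohorts × 4 periods × 2 = 16 placebo exposures.

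**4. Shift in the mean.** Using x/2 in place of x changes one value by -x/2, so the mean moves by -(x/2)/n whatever the other values are. For '<1.005' the numerator is 0.5025; for pH '<5.0' it is 2.5.

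| n | Shift, specific gravity | Shift, pH |
|---|---|---|
| 6 | -0.084 | -0.417 |
| 8 | -0.063 | -0.313 |
| 10 | -0.050 | -0.250 |
| 16 | -0.031 | -0.156 |

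**5. Mean and SD on assumed data.** The other specific gravity values are taken in order from 1.010, 1.012, 1.015, 1.018, 1.020, 1.022, 1.025, repeating as needed, plus one '<1.005'.

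| n | Mean, half limit | Mean, limit | SD, half limit | SD, limit |
|---|---|---|---|---|
| 6 | 0.930 | 1.013 | 0.209 | 0.0055 |
| 8 | 0.953 | 1.016 | 0.182 | 0.0067 |
| 10 | 0.965 | 1.015 | 0.163 | 0.0062 |
| 16 | 0.985 | 1.016 | 0.129 | 0.0060 |

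At n=8 the mean under the rule is (7.122 + 0.5025)/8 = 0.953. With the limit it is (7.122 + 1.005)/8 = 1.016. Every mean under the rule is below 1.000, and the SD is about 21 to 38 times larger. The median and first quartile are the same under both substitutions, because the censored value is the lowest either way. The minimum is 0.5025 instead of 1.005.

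For pH at n=8, with the others at 5.5, 6.0, 6.0, 6.5, 6.5, 7.0, 7.0, the mean is (44.5 + 2.5)/8 = 5.88 against (44.5 + 5.0)/8 = 6.19, and the SD is 1.46 against 0.70.

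**6. Error of the alternative.** A true specific gravity behind '<1.005' lies between 1.000 and 1.005. Substituting 1.005 is therefore wrong by at most 0.005, which at n=8 is 0.005/8 = 0.0006 in the mean. Substituting 0.5025 is wrong by at least 1.000 - 0.5025 = 0.4975, which is 0.4975/8 = 0.062 in the mean.

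**7. Where halving works.** For direct bilirubin '<0.1' with seven other assumed values (five at 0.1, two at 0.2), the n=8 mean is 0.119 with half the limit and 0.125 with the limit, and the SDs are 0.053 and 0.046. The fault is confined to scales that cannot approach zero.

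**The case against.** The strongest reply is that two conditions must both hold before anything happens, and the documents establish neither. First, a laboratory must report specific gravity or pH as '<x'. No reporting limit is given, and the rule speaks of a lower limit of quantification, which is an odd description of the bottom of a dipstick scale. Second, the parameter must be among the selected results of SAP 5.9.4, which are not listed; the mention of quantitative urinalysis concerns flagging. A mean of 0.95 for specific gravity would also be conspicuous when the tables are checked. All of this stands, and it is why the priority is low. It does not rescue the rule, which exists for precisely this contingency and gives an invalid number when triggered.

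A reader might infer more than the documents support:
- **Change from baseline.** SAP 4.1.2.4 defines the term, but SAP 5.9.4 does not request it for laboratory data. It is requested for vital signs (5.9.5) and ECGs (5.9.6).
- **Dilute urine from the water load.** The instruction in Protocol Table 20, "Repeat for confirmation approximately 1 hour after drinking a large glass (~250 mL) of water", concerns confirmatory repeats, and SAP 4.2.2 mentions unscheduled visits only for listings. The water taken before the urine β-2-microglobulin collection in Part B is not said to precede the same void as routine urinalysis.
- **Kidney monitoring and stopping.** The urinalysis triggers in Table 20 are protein, glucose and active sediment. The acute kidney injury and stopping criteria in Protocol 10.6 use serum creatinine, urine output and cystatin-C. None uses specific gravity, pH or a group mean.
- **INR.** Nothing suggests that it will be reported as '<x'.
- **A false treatment difference.** No hypothesis test is planned, the unaffected median is shown beside the mean, and the specific gravity value is too extreme to pass as an effect.

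**Conclusion.** The point holds in a limited form. As written, SAP 4.1.1.4 yields an impossible value for a censored specific gravity and an implausible one for a censored urine pH. One such specific gravity result would move a group mean by -0.031 to -0.084 over the planned group sizes, multiply the SD many times and put an impossible minimum in the table. The pH effect is milder: the mean shifts by 0.16 to 0.42 and the SD roughly doubles at n=8.

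This rests on assumed limits of 1.005 and 5.0, one censored value per group, and inclusion of the parameter in the selected summaries. If the laboratory never reports these parameters with '<', there is no effect. Medians and listings are not materially affected, and flags normally would not change, because a value below the reporting limit is low either way. Escalation and stopping decisions do not depend on these numbers. Low priority, but worth correcting because the error is in a stated rule and the remedy is simple.

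**What to change.** Add to SAP 4.1.1.4: *The half-limit rule applies only to concentration or activity results that can approach zero. For urine specific gravity and urine pH, a result reported as <x is set to x for descriptive summaries only, or the parameter is summarised by category. Low/normal/high flags are assigned from the reported result.*

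The flagging clause is needed because a result set to x could coincide with the lower limit of normal and then no longer count as below it. Leave the '>' rule unchanged, since its effect is negligible.

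The cost is a short addition to the SAP and one programming condition. Data collection and listings do not change.

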#### **4.1.1.5. Derived and Transformed Data**

There are no planned derivations or transformations.

#### **4.1.2. Definitions and Terminology**

##### **4.1.2.1. Screen Failure**

Screen failures are defined as subjects who consent to participate in the clinical trial but are not subsequently randomized in the trial.

##### **4.1.2.2. Analysis Period**

Given the crossover design of Part A, in which each unique subject receives four treatments in a randomly ordered sequence, Period 1 is the subset of study days between the start of dosing for the initial treatment in the sequence until the dosing for Period 2, the second treatment in the sequence. This includes the washout period between dose 1 and dose 2. Period 2 is the subset of study days between the start of dosing for the second treatment until the dosing for Period 3, including the washout period between dose 2 and dose 3. Period 3 is the subset of study days between the start of dosing for the third treatment until the dosing for Period 4, including the washout period between dose 3 and dose 4. Period 4 is the subset of study days between the start of dosing for the fourth period until the end of study.

##### **4.1.2.3. Age**

Age is defined as age at the time of signing the ICF.

##### **4.1.2.4. Baseline Value**

For purposes of analysis, the baseline value is defined as the last value obtained prior to initiation of IMP. For ECG via Holter monitoring, the baseline value will be the average of the -15, -30, and -45 timepoints.

##### **Period Baseline Value (Part A)**

For purposes of analysis of data within each Study Period, the period baseline value will be defined as the last valid evaluation done before the IMP administration within each of the treatment periods.

##### **Day 1 (Baseline) (Part B)**

Baseline for Part B (Day 1) is defined as the day IMP is first initiated.

##### **Period Day (Part A)**

For Part A, within each period, Period Day is defined relative to the first day of the sentinel dosing within each phase. Thus, the period day of an event is calculated as:

Period Day = event date – first date of period dosing (+1, if event date  $\geq$  date of Period Day 1)

This calculation will result in negative period days being assigned to visits occurring prior to treatment with IMP within each period, and positive study days being assigned on or after the start of IMP.

### **Study Day (Part B)**

Study Day is defined relative to Baseline (Day 1). Thus, the study day of an event is calculated as:

Study Day = event date – date of Day 1 (+ 1, if event date > date of Day 1).

This calculation will result in negative study days being assigned to visit occurring prior to the start of IMP and positive study days being assigned on or after the start of IMP. There will be no Day 0 value to match the schedule of events.

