#### 1.1.1. Part A (Single Ascending Dose: Cohorts 1 and 2)

Part A (Cohort 1 and Cohort 2) will employ a 4-period crossover, single ascending dose methodology. Up to 2 cohorts of participants may be evaluated during the Part A.

Cohorts 1 and 2 will be dosed in a sequential manner for up to 4 periods each. Progression to each dose level will occur following evaluation of all available cumulative safety, tolerability, PK, and other emergent data from the previous cohorts and periods.

The current trial may evaluate up to 8 different dose levels in Cohorts 1 and 2; however, some doses may be repeated, if required. The starting dose for Part A will be 0.5 mg. Doses, in general, will be escalated in Cohort 1 and Cohort 2 until the maximum tolerated dose is achieved or the CVL-354 exposures ( $C_{max}$  and  $AUC_{24}$ ) reach, or are projected to reach, the predefined human exposure limits [REDACTED]

[REDACTED] Dose escalation may also be stopped if it is determined that sufficient exposures are achieved, based on estimated target occupancy.

Based on emergent data, the actual doses may change; however, new doses will not exceed half-log increments (3.3-fold) from previous dose. Smaller increments (eg,  $\leq 2$ -fold) will be evaluated as exposures approach the proposed stopping criteria. All dosing decisions will be made jointly by the sponsor and the investigator after review of all available safety, tolerability (through 72 hours postdose), and PK data (through 24 hours postdose) at a Safety Review Team (SRT) meeting.

During dose escalation, Cohorts 1 and 2 will employ sentinel dosing (n=2; 1 CVL-354 and 1 placebo) during each period to ensure safety and tolerability before proceeding to dosing of non-sentinel participants for that period. The investigator will review AEs (serious and nonserious) and all available safety data from the first 24 hours after dosing for the 2 sentinel participants. If clinically significant safety concerns are observed in sentinel participants, dosing of the rest of the cohort will be paused in order for the SRT to discuss the findings and determine

subsequent actions. If no safety concerns are observed in the sentinel participants, the investigator will provide written documentation for sponsor confirmation before proceeding to dosing of non-sentinel participants.

[figure not shown]

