### 1.1.2. Part A (Food Effects: Cohort 3)

Cohort 3 will be scheduled after completion of single dose escalation to evaluate the effect of food on CVL-354 exposures after a single 50 mg dose. The selected dose is 4-fold lower than the top single CVL-354 200 mg dose that is considered to be safe and tolerated. For evaluation of food effect, a 2-period crossover design will be utilized, with approximately 8 participants randomized to 1 of 2 sequences (fed/fasted or fasted/fed). Sentinel dosing will not be employed for evaluation of food effect.

Participants will remain domiciled after Check-in for both periods of the food effect evaluation. The duration of each period will be 3 days, with a 2-day washout between Period 1 and Period 2.

The trial design for Part A (Food Effects, Cohort 3) is in [Figure 2](#).

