##### 4.1.1.2. Incomplete or Missing Dates

An incomplete date occurs when the exact date an event occurred or ended cannot be obtained from a subject. The database contains data fields for month, day, and year. A date is incomplete if at least one of these three fields is not known.

For many of the planned analyses, a complete date is necessary to determine if the event should be included in the analysis (ie, if the event is treatment-emergent) or to establish the duration of an event. In such cases, incomplete dates will be imputed.

For the purposes of handling partially reported start and stop dates for an event the following algorithm will be applied:

- Missing start day, but month and year present:
  - If the event occurs same month and year as the dosing of IMP, then the start day of the IMP will be assigned to the day of first dose of IMP.
  - Otherwise, the start day will be set to the first day of the month.
- Missing start day and month, but year present:
  - If event occurs in the same year as IMP dosing, then the start date of the event will be assigned to Day 1.
  - Otherwise, the start day and month will be set to 01 January.
- Missing all components of a start date:
  - Assign the date of Day 1.
- Missing end day, but month and year present:
  - The day will be set to the last day of the month.
- Missing end day and month, but year present:

- The end day and month will be set to the date of study completion/discontinuation.
- However, if study completion/discontinuation year is greater than the year of the event, then the day and month will be set to 31 December.
- In the event of a completely missing end date (year not present and ongoing not checked), the end date will be considered as ‘ongoing’ and will not be imputed.

If any imputed date causes the end date to occur prior to the start date of the event, the start date of the event will be used for the imputation of the end date. If any imputed date causes the start date of the event to occur after the end date of the event, the end date of the event will be used for the imputation of the start date. If the imputed date is later than the date of study withdrawal, then the date of study withdrawal will be imputed for the date. In subject data listings, start and stop date of events will be displayed as reported on the eCRF (ie, imputed values will not be listed).

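### Two SAP date rules are wrong as written (Part B Study Day gives a Day 0; partial AE start dates can put a Part A event under the wrong treatment), and the Period Day anchor is ambiguous

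*SAP*

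**What the plan says.** - **Study Day (Part B), SAP 4.1.2.** The formula is "Study Day = event date – date of Day 1 (+ 1, if event date > date of Day 1". The paragraph adds that days on or after the start of IMP are positive and that "There will be no Day 0 value to match the schedule of events". The preceding definition makes Day 1 the day IMP is first given, and Days on Study and Days on IMP count from Study Day 1.
- **Incomplete or missing dates, SAP 4.1.1.2.** For an AE whose start day is missing but whose month contains dosing, "then the start day of the IMP will be assigned to the day of first dose of IMP"; otherwise the first of the month is used. Year-only dates in a dosing year, and wholly missing dates, go to Day 1. No period is named. SAP 4.1.1.3 equates Day 1 with the first day of IMP, without limiting this to one part of the trial.
- **Attribution in Part A.** The treatment-emergent AE (TEAE) definition and SAP 5.9.1 assign each Part A event to a period and its treatment by start date.
- **Period Day (Part A), SAP 4.1.2.** The text says "Period Day is defined relative to the first day of the sentinel dosing within each phase". The formula subtracts the "first date of period dosing" and adds 1 on or after Period Day 1. The closing sentence promises "negative period days being assigned to visits occurring prior to treatment with IMP within each period".
- **Sentinels.** In Cohorts 1 and 2 the rest of the cohort waits for review of "all available safety data from the first 24 hours after dosing for the 2 sentinel participants" (SAP 1.1.1). For Cohort 3, "Sentinel dosing will not be employed for evaluation of food effect" (SAP 1.1.2).

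**The concern.** The Study Day formula contradicts its own paragraph and the parallel Part A formula, which uses ≥. A programmer who codes it literally produces a Day 0 and no Day 1.

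The partial-date rule is of the kind used in parallel-group trials, where the main question is whether an event began before or after the first dose. In a four-period crossover the imputed date may also decide the dose column. TEAEs by treatment are a primary safety summary. An event moved from a later, higher dose to Period 1 is counted at a lower dose or on placebo, and in a dose-escalation table that is the unhelpful direction.

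The Period Day text can be read from the sentinel's dosing date or from the participant's own, which gives different day labels for most SAD participants.

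**Working it through.** **1. Study Day (Part B).** Inputs: the SAP formula, and five cohorts of 10, so up to 50 participants (SAP 1.1.3).

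| Days from first dose | As written (>) | With ≥ |
|---|---|---|
| −2 | −2 | −2 |
| −1 | −1 | −1 |
| 0 | 0 | 1 |
| +1 | 2 | 2 |
| +13 | 14 | 14 |

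The SAP's stated result (no Day 0, positive from the start of IMP) is not reproduced by its formula. It is reproduced with ≥, and no other day changes.

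**2. Partial AE start dates in Part A.**

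*Year-only (dosing-year) or wholly missing dates.* Day 1 is read as the first day of IMP (SAP 4.1.1.3), so every such event goes to Period 1. Protocol Table 8 gives four sequences by four periods, or 16 cells per SAD cohort, with placebo once in each sequence and active doses rising:
- 4 cells (true Period 1) are unchanged.
- 6 move from an active dose to a lower active dose.
- 3 move from active to placebo.
- 3 move from placebo to the cohort's Period 1 active dose.

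These are cells, not weighted by how often events occur.

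*Month-only dates, one example.* Assume doses on 28 March and 2, 7 and 12 April, and an event on 8 April (true Period 3) recorded only as April.
- First trial dose date used only if it falls in the same month, otherwise the first of the month: 1 April, Period 1.
- First dose within that month: 2 April, Period 2.
- Day number of the first dose copied into the month: 28 April, Period 4.

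*Month-only dates, overall.* Assumptions: first dose on each of 365 calendar days; dose spacing s; onset uniform over s days in each of Periods 1 to 3 and over 15 days in Period 4; start day missing. The minimum s is 5 days (washout, SAP 1.1.1). The maximum is about 19: the Protocol synopsis gives up to 100 days including 28 of screening and 14 of follow-up, and (100 − 28 − 14)/3 = 19.3.

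| s (days) | Fits two or more periods | Moved earlier, first trial dose date used | Moved later, day number copied |
|---|---|---|---|
| 5 | 85.2% | 66.9% | 11.5% |
| 7 | 86.5% | 64.5% | 19.2% |
| 10 | 87.2% | 61.0% | 30.2% |
| 14 | 87.0% | 56.4% | 25.4% |
| 19 | 85.8% | 50.8% | 23.4% |

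With the first trial dose date, none moves later. Where an AE end date is known, the SAP's rule that a start may not follow the end would limit the moves in the last column.

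*Cohort 3.* Protocol Figure 2 puts check-out, which is Period 2 Day 3, on Day 8, so Period 2 dosing is Day 6. With 5 and 15 days of possible onset, 77.8% of month-only dates fit both periods, and 55.3% move from Period 2 to Period 1 when the first trial dose date is used. That swaps fed and fasted.

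**3. Period Day (Part A).** Take a non-sentinel dosed one day after the sentinels:

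| Event | Sentinel anchor | Own-dose anchor |
|---|---|---|
| Shared check-in | −1 | −2 |
| Sentinel dosing day | 1 | −1 |
| Own dose | 2 | 1 |
| Check-out (48 h) | 4 | 3 |

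On the sentinel anchor, the day before the participant's own dose is positive, so the closing sentence of the definition fails. With 6 non-sentinels of 8, this concerns 2 cohorts × 4 periods × 6 = 48 of 64 participant-periods if all eight periods run. On the own-dose anchor the count is 0.

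**The case against.** - **Study Day.** The paragraph states the intended result, so a careful programmer would probably get it right, and by-visit displays use nominal visits (SAP 4.2.2). A symbol lost in PDF conversion cannot be excluded; the signed file settles that. The text as supplied is still wrong.
- **Meaning of Day 1.** A reader might infer that Day 1 has no meaning in Part A, so that programmers would split freely on year-only and missing dates. The SAP does not support this: 4.1.1.3 ties Day 1 to the first day of IMP for the whole trial. The defect is that following this meaning sends those events to Period 1.
- **Direction.** A reader might infer that events can only move earlier. That holds when the first trial dose date is used, but not when its day number is copied.
- **Purpose.** SAP 5.9.1 invokes imputation to decide treatment emergence. A reader might infer that imputed dates play no part in period attribution. The SAP does not say so and names no other date for that step.
- **Size.** This objection largely stands. Participants are in clinic from Day −1 to Day 3 of each SAD period, and Cohort 3 is domiciled through both periods, so partial dates should be rare and mostly from washout or follow-up. Listings show dates as reported.
- **Period Day.** A reader might infer a flat contradiction between text and formula. If the period's first dosing date means the cohort's, the two agree and only the closing sentence fails, for non-sentinels. Either anchor mismatches some nominal label, so the choice is partly one of convention.

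**Conclusion.** The point holds as a minor correction.

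- The Part B Study Day formula is wrong as written. It affects first-dosing-day labels of up to 50 participants and no treatment comparison.
- The partial-date rule is wrong as written for Part A. It sends year-only (dosing-year) and wholly missing AE dates to the Period 1 treatment, and it can put month-only dates in the wrong period in either direction, depending on how the bullet is read.
- The Period Day anchor is ambiguous and changes day labels only. The sentinel sentence cannot apply to Cohort 3.

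The percentages rest on a partial date, uniform onset and the assumed spacings. They are not event rates, and the documents give no count of partial dates. A reader might infer that the TEAE tables will be materially biased; nothing in the documents shows that. Events dated before the first dose are outside this point.

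**What to change.** 1. **Study Day (Part B):** replace > with ≥, as in the Period Day formula.
2. **SAP 4.1.1.2:** in the month-only bullet, refer to the start day of the event rather than of the IMP, and say whether the full date of the first dose is meant. For Part A, restrict the imputed start to periods compatible with the known date parts, the AE end date and the participant's own dosing dates. If more than one period remains, apply one prespecified rule that does not depend on treatment. The period in which the event was recorded could serve, but only if the CRF captures it, which the documents do not show. Flag such events in the listing. A sensitivity TEAE table using the earliest compatible period is optional.
3. **Period Day (Part A):** state one anchor for Cohorts 1 to 3, for example the participant's own dose date, which matches how SAP 4.2.1 starts an analysis period. The shared check-in of later-dosed non-sentinels then becomes Period Day −2 or earlier, while its nominal Day −1 label stays.

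The cost is SAP wording and minor programming. No dose, visit or data collection changes.
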